The sample size calculation is based on a non-inferiority test of the difference between two means. Group sample sizes of 39 and 39 achieve 80% power to detect non-inferiority using a one-sided, two-sample t-test. The margin of non-inferiority is 10. Literature has shown that the minimum clinically significant difference in VAS pain score in children is 10-12 [65, 66] which is why 10 was chosen as our non-inferiority margin. The true difference between the means is assumed to be 5 based on the PICHFORK trial, which found a median rating reduction of 40 mm (IQR 20 to 45) at 30 minutes for fentanyl and a median rating reduction of 45 mm (IQR 20-60) at 30 minutes for ketamine, and therefore, a difference in medians of 5 (-10 to 20, 95% CI) [60]. Using the IQR information from the PICHFORK trial and assuming normality for the pain scores, we estimate the standard deviations to be 29.63 and 22.22 for the rating reduction at 30 minutes for the fentanyl and ketamine groups, respectively. Therefore, with an α of 0.05 and a β of 0.2 (80% power), the sample size required to detect this difference was estimated to be 39 subjects in each group, for a total of 78 subjects. In order to achieve this number of evaluable subjects, we plan to enroll 90 subjects, anticipating that not all subjects enrolled will be fully evaluable. Over the last year, there were 634 patients who presented to the CCHMC ED and were triaged as orthopedic evaluations. Of these, 360 were in the age group specified in the inclusion criteria. Given this data, we expect to be able to successfully complete this study as planned.

VII. STUDY PROCEDURES

Table 4. Study Procedures

Visits	Visit 1						Visit 2
	Screening Phase	Enrollment	15 (±5) min	30 (±5) min	60 (±5) min	120 (+30) min	+30 (±5) days *
Informed Consent, Assent for subjects ages 12-17		X					
Review Inclusion/Exclusion Criteria	X						
Demographics/Medical History	X						
Physical Examination	X						
Vital signs (HR, RR, BP, O2 sat)		X	X	X	X	X	
Serum or urine pregnancy test for postmenarchal females	X						
Weight	X						
VAS pain score		X	X	X	X		
UMSS sedation score		X	X	X	X		
Nasal mucosal exam	X					X	
Smell test	X					X	
Capnometry value		X	X	X	X		
Randomization		X					
Dispense study drug		X					
Adverse event/Serious adverse event assessment		X	X	X	X	X	X

*Visit 2 window +/- 5 days.

(See Appendix C for study flow diagram, Appendix D for current orthopedic evaluation flow diagram, and Appendix E for duration of study procedures)

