Additionally, data about missed eligible patients will be collected periodically through an EMR report and supplemented by chart review to assess screening hours, training needs or other issues that may inhibit staff's ability to enroll. We are requesting a HIPAA waiver to review the patient charts via the MRN and day/time of arrival and no information will be used for analysis in the research study. Consent would not otherwise be possible for these participants because of the nature of presentation to the ED; it is possible that these patients will have arrived when no study staff is available. Data collected on missed eligible patients will include MRN, encounter ID, date/time of ED arrival and discharge, means of arrival, date of birth, gender, whether or not they met study inclusion/exclusion criteria, disposition, discharge diagnosis, and provider name.

Primary Endpoint

The primary endpoint is the difference between the mean reduction in pain scores between the ketamine group and the fentanyl group as measured by the visual analog scale (VAS) at 30 minutes after study intervention.

The pain VAS is a unidimensional measure of pain intensity which has been widely used in diverse populations [66, 72, 73]. It is a continuous scale comprised of a horizontal or vertical line that is 10 cm (100 mm) in length anchored by two verbal descriptors representing pain extremes. The scale is most

commonly anchored by “no pain” (score of 0) and “pain as bad as it could be” or “worst imaginable pain” (score of 100). To avoid clustering of scores around a preferred numeric value, numbers or verbal descriptors at intermediate points are not present. The patient is asked to place a line perpendicular to the VAS line at the point that represents their current pain intensity. Using a ruler, the score is determined by measuring the distance (mm) on the 10-cm line between the “no pain” anchor and the patient's mark, providing a range of scores from 0–100. The visual analog scale has been shown to be valid and reliable in children 8 to 17 years of age suffering from acute pain and that a minimum clinically significant difference in VAS score ranges from 10 to 12 mm in children and adolescents [65, 66]. The optimal cut points for mild, moderate and severe pain on the VAS for children and adolescents have been determined to be 35 and 60 mm [1].

Secondary Endpoints

The secondary endpoints are to:

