Baseline and demographic characteristics will be summarized by standard descriptive summary statistics. This will include means and standard deviations for continuous variables expected to be normally distributed, such as age, vital signs, capnometry values, weight and VAS pain scores; proportions for categorical variables such as gender, race and injury location; and medians with ranges for variables expected to not be normally distributed, such as UMSS sedation scores. All continuous variables will be assessed for normality; parametric statistics will be used for normally distributed variables and non-parametric statistics will be used for non-normally distributed variables.

Efficacy Analysis

The primary analysis will include all subjects randomized based on the principle of intention to treat. If necessary, a per-protocol analysis will also be performed to assess efficacy of the treatments actually received. The primary efficacy endpoint will be the difference in mean pain scores between the ketamine group and the fentanyl group at 30 minutes after study intervention. This difference will be evaluated using the t-test.

Demographic and historical baseline information of the 2 study groups will be compared using t-tests (means), Mann-Whitney U (medians), and chi-square (proportions) tests. If there are any significant differences, linear regression will be performed to adjust for significantly different covariates.

For secondary outcomes, t-tests, or Mann-Whitney U where appropriate, will be used to evaluate differences in continuous outcomes (e.g. heart rate, blood pressure). Chi-square tests will be used to evaluate proportions in dichotomous outcomes (e.g. proportion with presence of specific adverse effects). Risk differences with 95% confidence intervals will be used to compare dichotomous outcomes such as the use of rescue analgesia and adverse events.

Safety Analysis

All subjects entered into the study will be included in the safety analysis. The frequencies of adverse events, including type, body system, severity and relationship to the study drug, will be summarized. We do not anticipate any serious adverse events. However, if one were to occur, it would be described in detail.

Adverse event incidence will be summarized along with the corresponding exact binomial 95% two-sided confidence intervals.

Test of Non-Inferiority

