A one-sided two-sample t-test will be used to test whether the pain reduction using ketamine is non-inferior to that of fentanyl. When the variances of the two groups are unequal, Welch's t-test will be used; if the data are not normally distributed, the Mann-Whitney (Wilcoxon signed rank) U test will be used [75, 76].

Interim Analysis

Due to the expected short duration of the study, no interim analysis will be performed. However, ongoing safety analysis of adverse events, serious adverse events and toxicities will be done.

IX. FACILITIES AND PERFORMANCE SITES

The study will be conducted at one investigative site in the United States. Cincinnati Children's Hospital Medical Center is an academic, freestanding, 523 bed children's hospital with 32,981 admissions and 125,130 Emergency Department visits annually. The population is diverse and includes 51% Caucasian, 40% African American, 2% Hispanic, and 7% other. Study enrollment will only be performed at the base campus.

X. POTENTIAL BENEFITS

Intranasal sub-dissociative dosing of ketamine has been shown in multiple studies to provide adequate analgesia to pediatric patients experiencing moderate to severe pain. Therefore, patients receiving the study medication may receive adequate analgesia and avoid the side effects associated with opioids and potentially the increased chance of adverse effects as a result of opioids in combination with ketamine procedural sedation later during their ED visit. Furthermore, patients who are genetically predisposed to have poor opioid sensitivity or those who have developed opioid tolerance due to other chronic painful conditions may find more benefit with the study medication.

XI. POTENTIAL RISKS, DISCOMFORTS, INCONVENIENCES and PRECAUTIONS

There are minimal risks associated with the administration of sub-dissociative ketamine via the intranasal route. All studies performed using intranasal ketamine at sub-dissociative dosing in children showed only minimal adverse events and no serious adverse events associated with the study medication. Examples of mild adverse events which could be expected to occur with both medications include drowsiness,

dizziness, pruritus, nausea, vomiting, dysphoria, unpleasant taste, vision changes, throat irritation, headache, and mild increase in heart rate and blood pressure.

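### An undefined normality check can move the primary non-inferiority analysis from a test of mean VAS reduction to a rank test with no stated margin

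*Combined protocol and SAP*

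**What the plan says.** Section VI (Sample Size and Power Analysis) rests on a one-sided two-sample t-test of a difference between two means, with α 0.05, 80% power and 39 evaluable children per arm. "The margin of non-inferiority is 10", in mm of VAS. Section VIII (Primary Endpoint) uses the same scale: "The primary endpoint is the difference between the mean reduction in pain scores between the ketamine group and the fentanyl group", at 30 minutes.

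Section VIII (Test of Non-Inferiority) names three tests. The default is a one-sided two-sample t-test, and Welch's version is used if the variances are unequal. The third is conditional: "if the data are not normally distributed, the Mann-Whitney (Wilcoxon signed rank) U test will be used". The margin is not restated for any of them.

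The Baseline Data paragraph of section VIII says that every continuous variable will be checked for normality and that "non-parametric statistics will be used for non-normally distributed variables". It lists "continuous variables expected to be normally distributed, such as age, vital signs, capnometry values, weight and VAS pain scores". Neither place names a normality test or a threshold, or says whether the check applies to each arm, to the pooled data or to residuals.

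The distributional evidence in the plan comes from the earlier paediatric trial cited in section VI. For the comparator arm it gives "a median rating reduction of 40 mm (IQR 20 to 45) at 30 minutes for fentanyl". The ketamine arm of that trial had a median of 45 mm, with quartiles of 20 and 60 mm.

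**The concern.** A non-inferiority conclusion needs one prespecified test tied to one margin on one scale. Here the scale can change. The t-test and Welch's test address the difference in means. A two-sample rank test asks whether values in one arm tend to exceed those in the other. The two questions coincide when the arms differ only by a shift, but not when they are skewed and differ in spread.

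The branching rule is written in advance but its trigger is not. Two analysts could follow the plan faithfully and reach different primary tests, and the choice could be settled with the outcome data in view. The trial's only primary conclusion would then rest on a test that the sample size was not built for.

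The branch is unlikely to be a remote contingency. The quoted quartiles are asymmetric in both arms, while section VI assumes normality to obtain its SDs.

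**Working it through.** **1. Reproduce the plan's figure.** Inputs from section VI: SDs 29.63 (fentanyl) and 22.22 (ketamine), true difference +5 mm (ketamine minus fentanyl), margin 10 mm, one-sided α 0.05.

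- Normal approximation: n = (1.645 + 0.842)² × (29.63² + 22.22²) / (5 + 10)² ≈ 37.7, so 38 per arm.
- SE at 39 per arm: √((29.63² + 22.22²)/39) = 5.931. The noncentral t with noncentrality 15/5.931 = 2.53 gives 80.6% power with pooled variance and 80.5% with Welch.

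So 39 per arm reproduces, for a test of means that uses the margin.

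**2. Asymmetry of the quoted reductions.** Quartile skew = (Q3 + Q1 − 2 × median)/(Q3 − Q1).

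- Fentanyl: (45 + 20 − 80)/25 = −0.60.
- Ketamine: (60 + 20 − 90)/40 = −0.25.

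A symmetric distribution gives 0. These children were aged 3–13 and received other doses (Table 2), so the figures are indicative only.

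**3. Rank test on normal data, stated SDs, 39 per arm.**

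| Test | Success at +5 mm | Success at −10 mm (error) |
|---|---|---|
| Welch with margin | 80.5% | 4.9% |
| Rank test, shifted by 10 mm | 78.6% | 5.2% |
| Rank test, no shift | about 20% | below 0.1% |

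On normal data the shifted rank test does little harm, but it is meant for data that are not normal.

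**4. Distributions matching the quoted quartiles.** Not in the plan and assumed here:

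- a quarter of each arm spread evenly over each of the four intervals cut by the quartiles;
- a lower end between −20 and 0 mm;
- an upper end of 60–80 mm for fentanyl and 75–90 mm for ketamine;
- Shapiro-Wilk at 5% in either arm as the check.

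Results over that range of end-points:

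- Rank branch entered in about 55–99% of trials (about 10% if the data are truly normal).
- Error at −10 mm, switching to a shifted rank test: about 5–10%. Welch alone: about 4–5%.
- Rank-test power at +5 mm if no shift were applied: about 25–37%. Welch on the same distributions: 79–94%.

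**5. What drives the direction.** More extreme shapes (gamma, shape 2; shape 4 lies between these and normal) were run with the stated SDs and with the SDs implied by the quoted IQRs: 25/1.35 = 18.5 for fentanyl and 40/1.35 = 29.6 for ketamine. Error at −10 mm, shifted fallback:

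| SDs (fentanyl / ketamine) | Skew | With switch | Always Welch |
|---|---|---|---|
| 29.63 / 22.22 | right | 12.7% | 6.1% |
| 29.63 / 22.22 | left | 1.8% | 4.3% |
| 18.5 / 29.6 | right | 1.1% | 4.2% |
| 18.5 / 29.6 | left | 19.6% | 6.5% |

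With equal SDs of 26.19 the shifted rank test stays at about 5%. The departure therefore needs both skew and unequal spread, and its sign depends on which arm is more variable.

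**The case against.** **A shift is implied.** The fallback stands under a non-inferiority heading, and the paragraph's first sentence gives its purpose. A reader might infer from the missing margin that the fallback is a superiority test with about 20% power. The documents do not support that as the natural reading: the same section omits the margin for the t-test and Welch's test too, and section VI supplies it once for the analysis. This objection stands. The power loss applies only if no shift were used.

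**The large error figures are extreme.** This also stands. Entry requires a VAS of at least 35 mm on a 0–100 scale, so no reduction can fall below 35 − 100 = −65 mm. A left-skewed gamma of shape 2 with SD 29.63 and an assumed mean reduction of 40 mm has its 0.1st percentile near −111 mm. The 1–20% range shows the mechanism, not the likely size. The quartile-matched 5–10% is the better guide.

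**The normality list concerns baseline.** The sentence naming VAS scores as normal describes baseline summaries, so it is not direct evidence about 30-minute reductions. That is fair. The point does not need it, because the non-inferiority section contains the switch itself.

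**Hypothesis #1.** Section II predicts no significant difference between the means. A reader might infer that a non-significant p-value would count as success. No section makes that a decision rule, and the objective directly above it is stated as non-inferiority. It is a wording inconsistency only.

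**A rank fallback is ordinary protection.** This does not stand here. At 39 per arm Welch's error stayed between about 4% and 7% in every scenario run, so the switch adds little protection and changes the question.

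**Conclusion.** The concern holds in moderate form and should be fixed. The textual part is firm: the trigger for changing the primary test is undefined, the margin is not attached to the fallback, and the fallback does not in general test the difference in means on which the endpoint and sample size are built.

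The size is less certain. On distributions resembling the only data the plan quotes, the switch raises false non-inferiority at the margin from about 4–5% to about 5–10%. That rests on an assumed check, assumed end-points and quartiles from other ages and doses. If the arms have equal spread, the error stays at about 5%. The documents do not show that the plan intends a superiority test or treats non-significance as success, and the sample size is not in question here.

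**What to change.** In section VIII (Test of Non-Inferiority), state that ketamine is non-inferior if the lower one-sided 95% Welch confidence limit for the difference in mean 30-minute VAS reduction (ketamine minus fentanyl) is above −10 mm, whatever the normality and variance checks show. Exempt the primary endpoint from the general switch in the Baseline Data paragraph.

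Keep a rank-sum test with 10 mm added to the ketamine reductions, or a Hodges-Lehmann limit compared with −10 mm, as a sensitivity analysis only. Correct the signed-rank label, which belongs to a paired test, to rank sum.

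Two wording alignments follow. Put the difference part of Hypothesis #1 in non-inferiority terms. Under Efficacy Analysis, "The primary efficacy endpoint will be the difference in mean pain scores between the ketamine group and the fentanyl group at 30 minutes" should refer to mean reduction, as the Primary Endpoint paragraph does.

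The cost is protocol and SAP text only. The sample size stays at 39 per arm: Welch power at +5 mm is 80.5% on the stated SDs and 84.3% on the IQR-derived ones. The mismatch between section VI's SDs and its own IQRs should be checked separately.

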Based on pharmacokinetic studies on intranasal ketamine use in children, the mean plasma concentrations peaked at about 20 minutes and the plasma concentrations of norketamine (the predominate active metabolite), peaked at about 120 minutes after administration of intranasal ketamine. Subjects will be observed in the emergency department for a minimum of 2 hours after study medication administration, thus providing resources and personnel for immediate, emergency care should the need arise. Those patients who are admitted and remain in the ED less than 2 hours will be monitored for the entirety of their ED stay. The admitting team will then be notified that they received a study medication. This length of observation is consistent with the amount of time that patients who are triaged as an orthopedic evaluation spend in the ED for standard therapy as most of these patients tend to remain in the ED for longer than two hours. This observation time does not pose any increased risk to the patient. Those patients discharged from the ED will be provided appropriate follow up instructions as per standard of care.

For these reasons, we expect enrollment in this trial to be of minimal risk to patients.

XII. RISK/BENEFIT ANALYSIS

Due to the prospect of direct benefit to patients and minimal risk to patients, the risk-benefit ratio seems favorable to patients, parents and providers.

XIII. DATA AND SAFETY MONITORING

Clinical Adverse Events

Clinical adverse events (AEs) will be monitored throughout the study. All adverse events will be followed until resolution.

Adverse Event Reporting

All on-site serious adverse events will be reported to the IRB in accordance with CCHMC IRB policies. Adverse Events will be reported to the IRB per CCHMC Research Policy R-18.

Definition of an Adverse Event

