Serious adverse event monitoring starts at the time of consent and ends at the time of discharge or admission. All SAEs will be followed until resolution, the event is considered to be medically stable, or for 30 days after the subject completes the study, whichever occurs first.

A distinction should be drawn between serious and severe AEs. A severe AE is a major event of its type. A severe AE does not necessarily need to be considered serious. For example, nausea which persists for several hours may be considered severe nausea, but would not be an SAE. On the other hand, a stroke that results in only a limited degree of disability may be considered a mild stroke, but would be an SAE.

Serious Adverse Events (SAEs) Specific to this Study

There has been documentation of a few significant adverse effects associated with the medications included in this study. These effects are exceedingly rare and are anticipated to be even rarer through an intranasal route of drug administration compared with an intravenous route and with sub-dissociative dosing of ketamine as compared with dissociative dosing.

Ketamine: cardiac arrhythmia, hypertensive emergency, prolonged emergence reaction, anaphylaxis, laryngospasm, apnea

Fentanyl: cardiac arrhythmia, cardiopulmonary arrest, chest wall rigidity, hypertensive emergency, hypotension, pulmonary embolism, anaphylaxis, apnea, bronchospasm, laryngospasm

In the exceedingly rare instance that one of these serious adverse effects was to occur, the patient would be treated for that particular emergency in a manner that is standard of care at CCHMC were the emergency to occur in any other setting.

Relationship of SAE to study drug or other intervention

The relationship of each SAE to the study intervention should be characterized using one of the following terms in accordance with CCHMC IRB Guidelines: definitely, probably, possibly, or unrelated.

Monitoring Plan

The medical monitor is the person responsible for the safety monitoring in this protocol and he will monitor all clinically significant adverse events (AEs) and provide consultation for any AEs that the investigators question the classification, severity or relatedness originally documented at the time of the ED visit. The medical monitor will be [name]. He is a member of the Division of Emergency Medicine, who will not be involved with enrollment.

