AEs will be reported to the IRB as detailed below. Adverse events will be recorded on the study data form by the study team. Any serious adverse events (SAEs) will be reported to the investigator or designee immediately. Study forms and charts will be reviewed by the study coordinator and principal investigator for AEs after the ED visit. All identified AEs will be recorded. The investigator will determine the grade and attribution. If unblinding is required, the investigator will notify the IRB. The protocol and consent will be reviewed by the investigator to determine if any changes are required. SAE's that are related to the study and unexpected will be reported to the IRB and FDA. Any serious adverse events and/or adverse events that occur during the study will be followed to resolution.

For the purpose of this study, toxicity is defined using the Common Terminology Criteria for Adverse Events (CTCAE) v4.0 as defined by the National Cancer Institute (<http://ctep.cancer.gov/reporting/ctc.html>).

Grade level 4 or greater toxicity which are unexpected and related to the study will be reported to the IRB within 48 hours. Examples pertinent to this protocol include: life threatening respiratory compromise resulting in intubation, anaphylaxis, hypotension, hypertensive crisis, life-threatening cardiac arrhythmias requiring urgent intervention, nausea and emesis with life-threatening consequences, and change in mental status including states harmful to the subject.

Subjects will be withdrawn from study drug exposure if any of the following events occur during the patient's stay in the ED:

- The subject has a SAE possibly or definitely related to the study drug
- The subject experiences a level 4 toxicity as defined by CTCAE
- The subject experiences one or more level 3 toxicities as defined by CTCAE
- The subject has an adverse event experience that would, in the investigator's judgment, make continued participation in the study not in the subject's best medical interest.

The trial will stop enrollment for the following events:

- A SAE rate related to the study intervention of greater than or equal to 2 in 10 subjects is detected
- Subjects experiencing grade 3 toxicities occur more frequently than 3 in 10 subjects.

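### Read as a cumulative rate, the related-SAE stop can trip on one event in the first five children yet lets five in thirty pass, in a protocol that anticipates no SAEs

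*Combined protocol and SAP*

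**What the plan says.** The Monitoring Plan in section XIII gives two events that stop enrolment. One is "A SAE rate related to the study intervention of greater than or equal to 2 in 10 subjects is detected". The other is "Subjects experiencing grade 3 toxicities occur more frequently than 3 in 10 subjects". Neither has a minimum denominator, a window, a pooled or per-arm basis, or a rationale. After a stop, a report goes to the IRB and FDA, and the IRB must approve any revisions before enrolment reopens.

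The expected level of harm is described elsewhere. Section VIII, Safety Analysis: "We do not anticipate any serious adverse events". Section XI says paediatric studies of sub-dissociative intranasal ketamine "showed only minimal adverse events and no serious adverse events associated with the study medication" and concludes that "we expect enrollment in this trial to be of minimal risk to patients". Section XIII lists serious effects of both drugs and says: "These effects are exceedingly rare". Section VI gives the size: "we plan to enroll 90 subjects".

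Other safeguards are ongoing safety analysis (section VIII, Interim Analysis), SAE reporting within 24 hours, a medical monitor, and reporting to the IRB and FDA (section XIII).

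**The concern.** A stopping rule in a low-risk trial exists for harm that nobody expects. Read as a cumulative rate, this one behaves unevenly. It is very sensitive for the first five children, where a single related event is already 20%. After that it allows a number of related SAEs far above anything the protocol foresees.

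The rule already excludes the obvious source of background events. It counts only related SAEs, and admission for injury repair or pain management is not an SAE under section XIII. Expected orthopaedic admissions therefore do not explain a 20% threshold.

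The subject-level rule does not help later children. It reads "Subjects will be withdrawn from study drug exposure if any of the following events occur", but each child receives a single study dose, so by then the exposure has happened. The two rates are the only numeric limits in the protocol on dosing further children. What is at stake is how many children are dosed before a review is required.

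**Working it through.** The plan states no operating characteristics for these rules, so there is no figure of its own to reproduce.

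**Inputs.** SAE rule: stop if events/dosed ≥ 0.20. Grade 3 rule: stop if > 0.30 (both section XIII). N = 90 (section VI). The true related-SAE rates *p* are assumptions; the documents give none. Events are taken as independent, both arms pooled, with a check after every child.

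**Step 1: counts, with no assumed rate.** One event in 5 is 1/5 = 20% and stops; one in 6 is 16.7% and does not. The largest *k* with *k* < 0.2*n* is:

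- *n* = 20: 3 (15.0%)
- *n* = 30: 5 (16.7%)
- *n* = 45: 8 (17.8%)
- *n* = 90: 17 (18.9%)

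These counts can be reached without an earlier crossing. If event *k* falls on child 5*k*+1, then *k*/(5*k*+1) < 0.20 at every event; the fifth falls on child 26 and the seventeenth on child 86. For grade 3 toxicity the largest *k* ≤ 0.3*n* is 6, 9, 13 and 27.

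**Step 2: chance of a stop, cumulative reading.** Let f(n,k) be the probability of *k* events in *n* children with no stop so far. Then f(n,k) = (1−p)·f(n−1,k) + p·f(n−1,k−1), kept only where k/n < 0.20. The chance of a stop is 1 − Σₖ f(90,k).

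Hand check: the chance of stopping within the first five children is 1 − (1−p)⁵. At 5% that is 1 − 0.95⁵ = 22.6%, out of 25.0% for the whole trial. At 10% it is 41.0% out of 50.0%. Nearly all of the rule's sensitivity lies in the first five children.

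**Step 3: the other reading.** Suppose the rule means two related SAEs within any ten consecutive children. Track the number of children since the last event; a new event stops the trial if the previous one was among the preceding nine children.

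**Step 4: cumulative rule plus a pause at the third related SAE.** As step 2, also requiring *k* ≤ 2. Hand check at 5% for the count alone: 1 − [0.95⁹⁰ + 90(0.05)(0.95⁸⁹) + 4005(0.05²)(0.95⁸⁸)] = 1 − (0.010 + 0.047 + 0.110) ≈ 83%. Early stops by the rate rule bring it to 85%.

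| Assumed true rate | Expected related SAEs in 90 | Cumulative rule | Two in any ten | Cumulative rule + third-SAE pause |
|---|---|---|---|---|
| 0.5% | 0.45 | 2.5% | 1.8% | 3.4% |
| 1% | 0.9 | 5% | 6.6% | 10% |
| 2% | 1.8 | 10% | 22% | 32% |
| 5% | 4.5 | 25% | 71% | 85% |
| 10% | 9 | 50% | 98% | 99.6% |

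**Step 5: would a minimum denominator help?** Starting the rate rule at the tenth child lowers its chance of stopping at a true 5% from 25% to 9.7%. With a tenth-child start plus a third-SAE pause, the chance of a halt within the first nine children at 5% is 0.8%, against 24% under the literal rule. A minimum removes early protection.

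**The case against.** The strongest objection is the reading. Two in ten subjects can be taken as two events among ten children, and on that reading the rule is already strong from about 2% upwards. This stands as a reason for the protocol to state which it means. It does not displace the cumulative reading, because the text speaks of a rate and defines no block or window.

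Second, the formal rule is not the only protection. The ongoing safety analysis, 24-hour reporting, the medical monitor and IRB and FDA reporting could each lead to a halt well before 20%, and the local IRB policies the protocol relies on are not in the documents. This also stands. As written, though, these act by discretion, and the protocol ties none of them to a number or a pause.

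Third, a reader might infer that 17 related SAEs in 90 would be an ordinary outcome, or that the sponsor would keep dosing through them. The documents do not support that. Seventeen is the arithmetical limit and needs events spaced almost evenly. The chance of finishing unstopped with exactly 17 is below 1% at true rates of 10%, 15% and 20%, and the discretionary safeguards would have acted or been available long before.

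Finally, the choice of the third event is a judgement, since the protocol names no related-SAE rate it would find unacceptable.

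**Conclusion.** The point holds as a low-cost safety improvement to consider. On the cumulative reading the SAE stop is erratic early and permissive later: one event in five children meets it, five in thirty do not, and it stops only a quarter of trials at a true 5% rate and half at 10%. The counts need no assumption. The percentages rest on the assumed rates, independent events, pooled arms and a check after each child. On the two-in-any-ten reading the permissiveness largely disappears and only the ambiguity remains.

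Nothing here shows that either drug is unsafe or that related SAEs are likely. If none occurs the rule never matters, and the non-inferiority analysis is unaffected either way.

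**What to change.** Keep both rate rules in force from the first child, with no minimum number dosed. State whether the SAE rule is a cumulative proportion or two events within any ten consecutive children. Then add one sentence to the stopping rules in section XIII:

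*Dosing also pauses at the third SAE judged possibly, probably or definitely related, whatever the number dosed, both arms together and blinded, until the medical monitor has reviewed it and the IRB agrees to resume.*

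Naming the three categories matters because the relationship scale includes probably, while the subject-withdrawal criterion mentions only possibly and definitely.

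The change needs no new staff and no unblinding, and the protocol already has an IRB step before enrolment reopens. It costs more reviewable pauses at low but non-zero rates: the chance of a halt rises from 2.5% to 3.4% at a true 0.5%, from 5% to 10% at 1%, and from 10% to 32% at 2%. If the sponsor would accept a 2% rate without review, a later trigger is reasonable and the protocol should give that reason. Pooling the arms preserves the blind but can dilute a signal confined to one drug; the medical monitor's review should take that into account.
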